#### h) Central lab

i) Confirmation for Chagas diagnosis tests with 2 different serological tests are allowed to be performed during Screening only if there is no documented historical diagnosis.

j) Qualifying LVEF measurements/documentation will be based on any local measurement (using echocardiography, MUGA, CT scanning, MRI, or ventricular angiography) performed  $\leq 12$  months prior to Visit 1. An echocardiography is allowed to be performed during Screening only if there is no previous ejection fraction measurement (within 12 months).

k) For participants included in the biomarkers additional assessment, blood samples will be collected at Randomization, Week 6 and Month 8 as described in the laboratory manual. The samples will be processed by a central laboratory and then shipped to and stored in the Novartis repository. For participants included in the biomarkers assessment after the baseline visit, samples can be collected according to detailed in the lab manual.

l) For participants in the Holter monitoring additional assessment

m) For participants in the MRI additional assessment

## **8.1 Screening**

### **8.1.1 Information to be collected on screening failures**

Participants who sign the model informed consent form and subsequently are found to be ineligible prior to randomization will be considered screen failures. The reason for screen failure should be recorded on the appropriate eCRF. The demographic information, informed consent, and inclusion/exclusion pages must also be completed for screen failures. No other data will be entered into the clinical database for screen failures, unless the participant experienced an SAE during the screening phase (see [Section 10.1.3](#) for reporting details). If the participant fails to be randomized, the IWRS must be notified within 2 days.

Participants who are randomized and fail to start treatment, e.g., randomized in error, will be considered early terminators. The reason for early termination should be recorded on the appropriate eCRF.

Reporting of SAEs during the Screening Epoch should be followed as described in [Section 10.1.2](#). The Adverse Events eCRF page should be completed for any SAEs that occur during the Screening Epoch.

Potential AEs and hospitalizations that are not SAEs which may have occurred from the time of signing the informed consent until the time of failed screening will be followed by the Investigator and collected only in the source data.

If a participant discontinues prior to Randomization, the IWRS provider should be notified, and the reason for the participant not being randomized entered on the Screening Epoch Disposition eCRF page. The screening visit date, the Demography eCRF page, the Informed Consent eCRF page, and the Inclusion/Exclusion eCRF page must be completed.

The Withdrawal of Consent eCRF page must be completed if consent is withdrawn during the Screening Epoch before the participant is randomized.

Investigators will have the discretion to record abnormal test findings on the Medical History eCRF page whenever, in their judgment, the test abnormality occurs before the informed consent is signed.

### **Re-screening**

Participants who enter Screening, but are determined not to be eligible to be randomized will be considered screen failures. Investigators may consider re-screening the participants at a later time if they believe that their condition has changed and they may potentially be eligible. In this case, new participant numbers will be allocated to the participants and they will need to have Visit 1 again.

Participants may be re-screened up to 2 times. A minimum of 2 weeks must elapse between re-screenings. Participants must provide new written informed consent each time they are re-screened.

## **8.2 Participant demographics/other baseline characteristics**

Country-specific regulations should be considered for the collection of demographic and baseline characteristics in alignment with the eCRF.

Demographics and baseline characteristics data to be collected on all participants include date of birth (according to local laws and regulations), age, sex, race, ethnicity, and source of participant referral.

Relevant medical history/current medical condition data include data until the first administration of study drug. Where possible, diagnoses will be recorded, and not symptoms. HF medications and other CV medications will be recorded in eCRFs separate from other medications. Likewise, detailed HF history and other relevant CV medical history will be recorded on eCRFs separate from other medical history.

### **8.2.1 Smoking history**

The current and/or previous use of tobacco products will be recorded, as well as the estimated number of pack-years based on the approximate consumption per year. Non-smokers will be advised not to start smoking during the study.

### **8.2.2 Relevant medical history/current medical conditions**

Relevant medical history and current medical conditions prior to signing of the informed consent will be recorded in the Medical History eCRF page. Whenever possible, diagnoses and not symptoms will be recorded.

Significant findings that are observed after the participant has signed the model informed consent form and that meet the definition of an AE must be recorded in the Adverse Event eCRF page.

### **8.2.3 Prior and concomitant medications**

Concomitant medications and prior medications taken within the 6 months preceding study enrollment will be captured at the Screening Visit, and updated at the Randomization Visit.

## **8.3 Efficacy**

### **8.3.1 Time from randomization to CV death, or time to the first HF hospitalization, or relative change from Baseline to Week 12 in NT-proBNP**

Time to CV death, time to first HF hospitalization, and the relative change in NT-proBNP between Baseline and Week 12 will be determined.

The analysis will be done in a hierarchical order: time to CV death (worst category; earlier time to CV death is unfavorable), time to first HF hospitalization (second worst category; earlier time to HF hospitalization is unfavorable) and the relative change from Baseline to Week 12 in NT-proBNP (best category; more reduction or less increase). In order to differentiate the response in NT-proBNP, the difference needs to be +/- 25%.

This margin was chosen based on PARADIGM-HF data, where a 25% reduction in NT-proBNP was associated with a 15% hazard reduction for the occurrence of a first HF hospitalization or CV death, therefore, it can be considered clinically meaningful, i.e., a ‘winner’ in an NT-proBNP based comparison is only declared if the relative change of NT-proBNP from Baseline differs for more than 25% between two participants (more reduction or less increase).

#### **8.3.2 Time from randomization to the first occurrence of a composite of CV events**

The time to the first occurrence of the composite of HF hospitalization or CV death will be determined.

#### **8.3.3 Time from randomization to all-cause mortality**

The time to all-cause mortality will be determined.

#### **8.3.4 Time from randomization to sudden death or resuscitated sudden cardiac arrest**

The time to sudden death or resuscitated sudden cardiac arrest will be determined.

#### **8.3.5 Number of visits to an ER due to HF**

The rate of visits to an ER due to HF (where intravenous therapy is required) will be determined.

#### **8.3.6 Number of days alive out of the hospital**

The number of days alive out of the hospital will be determined.

#### **8.3.7 Number of ventricular fibrillation or sustained ventricular tachycardia needing specific pharmacological, electrical or other treatment**

The number of ventricular fibrillation or sustained ventricular tachycardia needing specific pharmacological, electrical, or other treatment will be determined.

#### **8.3.8 Number of anti-tachycardia pacing or shock therapies**

This will be determined in a subset on a subset of participants who have an ICD or CRT-D at Randomization.

#### **8.3.9 Appropriateness of efficacy assessments**

The measurements are standard for the type of study being performed.

### **8.4 Safety**

Safety assessments are specified in [Table 8-2](#) with the assessment schedule detailing when each assessment is to be performed.

For details on AE collection and reporting, refer to AE section.

**Table 8-2 Assessments and specifications**

Assessment	Specification
Physical examination	
A complete physical examination will be performed at Visit 1 and at yearly intervals thereafter until the End-of-study Visit. It will include the check of general appearance, skin, neck (including thyroid), eyes, ears, nose, throat, lungs, heart, abdomen, back, lymph nodes, and extremities, vascular and neurological exploration. If indicated based on medical history and/or symptoms, exams of rectum, external genitalia, breast, and pelvic will be performed.
 
A short physical examination will be performed, except where a complete physical examination is required (see Table 8-1) and will include the check of general appearance and vital signs (blood pressure and pulse).
 
Information about all physical examinations must be present in the source documentation at the study site. Significant findings that are present prior to the start of study drug must be included in the Relevant Medical History/Current Medical Conditions eCRF page. Significant findings made after the start of study drug which meet the definition of an AE must be recorded on the Adverse Events eCRF page.

Vital signs	
Vital signs will be assessed at every visit and will include sitting measurements of blood pressure and pulse. Blood pressure will be measured on the non-dominant arm after 5 minutes of rest using a standard sphygmomanometer with an appropriate size cuff.
 
Normal blood pressure will be defined as systolic pressure of 90 to < 120 mmHg, and diastolic blood pressure of 60 to < 80 mmHg under the measurement conditions outlined above. Notable blood pressure findings will be hypertension (systolic blood pressure of <math>\geq</math> 140 mmHg and/or diastolic blood pressure of <math>\geq</math> 90 mmHg) or hypotension (systolic blood pressure of < 90 mmHg and/or a diastolic blood pressure of < 60 mmHg). A blood pressure indicative of prehypertension (systolic blood pressure of 120 to < 140 mmHg and/or diastolic blood pressure of 80 to < 90 mmHg) will not be regarded as notable.
 
A normal pulse rate will be defined as a rate of 60 to 100 beats per minute (bpm) under the measurement conditions outlined above. Notable pulse rate will be a rate below 60 bpm (bradycardia) or above 100 bpm (tachycardia).
 
Whether action needs to be taken to address notable vital signs will be decided by the Investigator, taking into account the overall status of the participant. No specific action is foreseen as part of the study protocol.

#### 8.4.1 Laboratory evaluations

A central laboratory will be used for the efficacy analysis of NT-proBNP (at randomization and Week 12 visit). No reconciliation with the central laboratory will be done for the local NT-proBNP used during the screening epoch. Details on the collection, shipment of samples and reporting of results by the central laboratory are provided to Investigators in the laboratory manual.

For the remaining laboratory evaluations only local laboratory will be used. Laboratory values will not be entered in eCRF (except NT-proBNP from screening).

Clinically notable laboratory findings are defined in [Appendix 1](#).

Complete safety laboratory evaluations ([Table 8-3](#)) will be performed in the fasting state at the times indicated in [Table 8-1](#).

Study procedures may be performed without restriction while the local laboratory results are pending. In these cases, the Investigator or designee should review the local laboratory results

as soon as they become available to decide whether any adjustments in the participant's study drug or non-study drug regimen are needed.

The Investigator must assess laboratory values that exceed the boundaries of notable laboratory abnormality and perform additional laboratory evaluations as judged appropriate. If the laboratory abnormality is the primary reason for an unforeseen hospitalization or otherwise fulfills the seriousness category of an AE, then the procedure for rapid notification of SAEs must be followed. Likewise, if the laboratory abnormality leads to discontinuation from the study drug (temporarily or permanently), the participant must be followed until the abnormality resolves or until it is considered permanent. The investigation may include continued monitoring by repeat laboratory testing or by additional laboratory tests as deemed necessary by the Investigator or the ARO/Novartis medical monitor.

**Table 8-3 Laboratory assessments**

Test category	Test name
Hematology	Hemoglobin, hematocrit, red blood cell count, white blood cell count with differential, and platelet count will be quantified.
Chemistry	Blood urea nitrogen, glucose, creatinine, total bilirubin, aspartate, aminotransferase, alanine aminotransferase, alkaline phosphatase, sodium, potassium, and chloride will be measured.
Additional tests	Blood samples will be obtained at the times indicated in Table 8-1 to determine changes in NT-proBNP (details will be provided in the laboratory manual).
Pregnancy test	All female participants of childbearing potential will have a serum pregnancy test performed at Visit 1. Additionally, these participants will have urine pregnancy tests performed at the times indicated in Table 8-1 . In case of a positive urine pregnancy result, a confirmatory serum pregnancy test will be performed at the local laboratory.

#### **8.4.2 Electrocardiogram**

A standard 12-lead ECG will be performed at Screening (Visit 1), and at the times indicated in [Table 8-1](#). Interpretation of the tracing must be made by a qualified physician and documented on the Electrocardiogram eCRF page. Each ECG tracing should be kept in the source documents at the study site labeled with study number, participant initials, participant number, and date. Any identifier details (e.g., participant initials, date of birth) must be redacted from all ECGs.

Only clinically significant abnormalities should be reported on the Electrocardiogram eCRF page. Clinically significant abnormalities should also be recorded on the relevant Medical History/Current Medical Conditions or Adverse Events eCRF page.

For any ECGs with participant safety concerns, 2 additional ECGs must be performed to confirm the safety finding. A monitoring or review process should be in place for clinically significant ECG findings throughout the study and especially at Randomization before administration of study treatment.

In the event that a clinically significant ECG abnormality is identified at the study site (e.g., severe arrhythmia, conduction abnormality, or QTcF > 500 ms), a copy of the assessment is to be sent to the local laboratory for expedited review if applicable, and the ECG is repeated to

confirm the diagnosis. If the participant is hemodynamically compromised, the Investigator or a medically qualified person must initiate appropriate safety procedures without delay (for example cardioversion).

Clinically significant abnormalities must be recorded on the eCRF as either medical history/current medical conditions or AEs as appropriate.

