**Table 8-1 Assessment schedule events**

		Titration Period				Follow-up Period *							
Visit number	1	101	102	103	104	105	106	107	108 a	109	110	111 112... f	199 EOS
Time of visit (Day [D], Week [W], Month [M])	SC	D1	W3	W6	W9	W12	M4	M8	M12	M18	M24	M30 M36... f	
Inclusion/exclusion criteria	X	X											
Informed consent	X												
Randomization		X b											
Vital signs	X	X	X	X	X	X	X	X	X	X	X	X	X
Demographics, medical history	X												
Physical examination c	S	S	S	S	S	S	S	S	S	S	S	S	S
Height	X												
Weight	X	X	X	X	X	X	X	X	X	X	X	X	X
NYHA class (HF signs & symptoms)	X	X	X	X	X	X	X	X	X	X	X	X	X
Abbreviated chemistry d	S		S	S	S	S	S	S	S	S	S	S	S
Serum/urine pregnancy tests e	S	S	S	S	S	S	S	S	S	S	S	S	S
Dispense study medication		X	X	X	X	X	X	X	X	X	X	X	X
Study drug accountability			X	X	X	X	X	X	X	X	X	X	X
HF and CV medications	X	X	X	X	X	X	X	X	X	X	X	X	X
Concomitant medications	X	X	X	X	X	X	X	X	X	X	X	X	X
Adverse events		X	X	X	X	X	X	X	X	X	X	X	X
Record HF hospitalizations			X	X	X	X	X	X	X	X	X	X	X
NT-proBNP	(X) g	X h				X h		X k					

		Titration Period				Follow-up Period *							
Visit number	1	101	102	103	104	105	106	107	108 a	109	110	111 112... f	199 EOS
Time of visit (Day [D], Week [W], Month [M])	SC	D1	W3	W6	W9	W12	M4	M8	M12	M18	M24	M30 M36... f	
Twelve-lead ECG	X												X
Chagas diagnosis test i	(X)												
Echocardiography j	(X)												
Biomarkers k		X		X				X					
Holter monitoring l		X						X					
Magnetic resonance imaging m		X						X					

EOS: end of study, SC: screening (Day -14 to Day -1) X = assessment to be recorded on clinical data base

S = assessment to be recorded on eSource/source documentation only

\* If the study is extended, Visits 113, 114 and so forth to be performed at the same intervals and with same measurements as at visits 109, 110, and so forth.

\*\* In case of Public Health emergency as declared by Local or Regional authorities (i.e. pandemic) and participants are unable for complete study visits at the site, site staff should do all the efforts to collect at least safety information from the participants by phone in order to confirm unreported SAEs. Also IP delivery at participant's home may also be arranged in order to ensure treatment continuity.

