## **Twelve-lead ECG**

All ECG data will be listed by treatment arm, participant, and visit/time, abnormalities will be flagged. Summary statistics will be provided by treatment and visit/time.

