2.6.3.2 Twelve-lead ECG

All ECG data (Rhythm, P-wave duration, Heart rate, QRS Complex Duration, QT Interval, will be listed by treatment arm, subject and visit (Baseline and EOS), abnormalities (Pathological Q Waves, Left anterior fascicular block, Posterior fascicular block, Complete Left Bundle Branch Block, Right Bundle Branch Block, Left Ventricular Hypertrophy, Low QRS voltage) will be flagged. Summary statistics will be provided by treatment at V1 and EOS.

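### Protocol 8.4.2 gives conflicting rules on which ECG findings reach the eCRF, although all ECG data are to be summarised by arm; and the SAP names raw QT but no QTcF

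*Protocol*

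**What the plan says.** Protocol 8.4.2 contains two instructions for one eCRF page. The first has no restriction to abnormal tracings: "Interpretation of the tracing must be made by a qualified physician and documented on the Electrocardiogram eCRF page". The second follows in the next paragraph: "Only clinically significant abnormalities should be reported on the Electrocardiogram eCRF page".

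Table 8-1 schedules the 12-lead ECG at Visit 1 and at EOS and marks both with X. Its key reads "X = assessment to be recorded on clinical data base". The alternative code, not used for the ECG row, reads "S = assessment to be recorded on eSource/source documentation only".

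On analysis, Protocol 12.5.2 plans: "All ECG data will be listed by treatment arm, participant, and visit/time, abnormalities will be flagged", with summary statistics by treatment and visit. SAP 2.6.3.2 names the variables (rhythm, P-wave duration, heart rate, and then "QRS Complex Duration, QT Interval, will be listed by treatment arm, subject and visit (Baseline and EOS"). It flags seven named abnormalities, among them the fascicular and bundle branch blocks, and adds: "Summary statistics will be provided by treatment at V1 and EOS".

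On corrected QT, Protocol 8.4.2 gives examples of a clinically significant abnormality found at the site: "severe arrhythmia, conduction abnormality, or QTcF > 500 ms". Such a finding leads to a repeat ECG and, where applicable, expedited review. The SAP repeats this text as the footnote to the arrhythmia row of its Table 4. SAP 2.6.3.2 does not mention QTc or QTcF.

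**The concern.** A summary of heart rate, QRS or QT by arm means something only if the values come from all participants with a tracing, or from a subset chosen by a known rule. If a site enters only what it judges clinically significant, the table describes unusual tracings. Its denominator depends on local opinion, and a long-standing bundle branch block is counted at one site and left out at another. A participant entered at only one of the two visits contributes no change from V1 to EOS.

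The trial is open-label (Protocol 4.1 and 6.4), so the judgement at EOS is made by staff who know the treatment. The ECG is a listed safety parameter in Protocol Table 2-1, and Protocol 1.1 describes a disease marked by conduction-system damage and frequent ventricular arrhythmia. The table is therefore one that readers will look at.

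The QT item is separate. Raw QT varies with heart rate, so a table of raw QT does not show how many participants in each arm pass the one QT value that the documents mention.

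**Working it through.** There is no stated figure to reproduce. The check is mainly a comparison of texts, with one short conversion for QT.

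**1. What each text implies for a tracing judged not clinically significant**

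| Text | Is it in the database? |
|---|---|
| Protocol 8.4.2, interpretation sentence | The interpretation is; measurements are not mentioned |
| Protocol 8.4.2, restrictive sentence | Not, if read literally |
| Protocol Table 8-1, code X at V1 and EOS | Yes |
| Protocol 12.5.2, all ECG data listed and summarised | Yes |
| SAP 2.6.3.2, named intervals and abnormalities summarised | Yes |

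The restrictive sentence stands alone against the other four. Three of those four are in the protocol, so the conflict starts there and the SAP inherits it.

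**2. Can the two sentences in 8.4.2 be reconciled?** Partly. The restrictive sentence could govern only which abnormalities are reported and leave rhythm and intervals to be entered for everyone. Even then, the abnormalities flagged in the SAP would be counted only when a site calls them significant. Nor does either document say that numerical rate, QRS and QT are entered for every tracing; an interpretation is not a set of measurements.

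**3. Comparison with laboratory data.** Protocol 8.4.1 says that laboratory values, apart from screening NT-proBNP, are not entered in the eCRF. SAP 2.6.4 follows this and plans no summary of them. Collection and analysis agree there. For the ECG, no text brings them into line.

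**4. Where knowledge of treatment can enter.** ECGs are scheduled at V1 and EOS only. V1 precedes randomisation, so selection there cannot depend on the assigned arm. Only selection at EOS can.

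**5. Raw QT against QTcF.** The documents print no formula. Assume Fridericia: QTcF = QT / RR^(1/3), with RR = 60 / heart rate in seconds. Then QTcF = 500 ms corresponds to QT = 500 × (60 / heart rate)^(1/3). The heart rates below are assumptions chosen to show the range.

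| Heart rate (bpm) | QT at which QTcF = 500 ms | QTcF when QT = 500 ms |
|---|---|---|
| 50 | 531.3 ms | 470.5 ms |
| 60 | 500.0 ms | 500.0 ms |
| 80 | 454.3 ms | 550.3 ms |
| 100 | 421.7 ms | 592.8 ms |

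A summary of raw QT therefore cannot stand in for a count above QTcF 500 ms. Since SAP 2.6.3.2 lists both QT and heart rate, QTcF can be derived for each tracing on which both are recorded.

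**The case against.** The strongest case against is that the data are probably in the database. Table 8-1 uses the database code, the interpretation goes on the ECG page, and SAP version 2.1 names items as specific as P-wave duration and low QRS voltage, which suggests that fields exist for them. When the sponsor meant values to stay at the site, as with laboratory results, it said so. This stands as far as it goes: it makes loss of data less likely. It does not remove the contrary sentence, which a site may have followed.

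Important signals also have other routes. Clinically significant abnormalities go to the adverse event or medical history pages. Arrhythmia is an event of special interest with its own form and a between-arm comparison (SAP 2.6.3.4). Treated ventricular fibrillation or sustained tachycardia and sudden death or resuscitated arrest are separate endpoints. This stands too, and it limits the consequence.

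On QTcF, 500 ms is introduced only as an example for site action, and Protocol 4.5.1 does not name QT prolongation among the main risks. The variable list in SAP 2.6.3.2 also has an unclosed bracket and a stray comma, so an item may have been lost in drafting or extraction. The request for QTcF is thus a low-cost improvement, not the repair of a declared criterion that was forgotten.

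A reader might infer more than the documents support:

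- That ECG values are missing. This would need the eCRF, which is not available.
- That knowledge of treatment shaped selection at both visits. It cannot have done so at V1.
- That the 500 ms value cannot be tabulated. It can, from variables already listed.
- That a given arm difference would be masked by a given amount. The documents give no QT distribution and no numerical rule for what a site calls significant.

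**Conclusion.** The point holds as a conflict of instructions with an uncertain consequence. The restrictive sentence in Protocol 8.4.2 is at odds with its neighbouring sentence, with Table 8-1, with Protocol 12.5.2 and with SAP 2.6.3.2. If sites followed it, the by-arm ECG summaries and block counts come from a subset selected by site judgement, with treatment known at EOS only. If they did not, the wording needs correcting and the table is sound. The documents do not settle which, and no magnitude can be attached.

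The absence of corrected QT from SAP 2.6.3.2 holds for the text as extracted. Its practical content is that the planned table does not show the number of participants above the one QT value mentioned in the documents.

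Both parts concern descriptive safety output. The primary analysis, type I error and sample size are untouched.

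**What to change.** 1. **Protocol 8.4.2.** Reword so that rhythm, heart rate, P-wave duration, QRS, QT and the abnormalities listed in the SAP are entered for every participant at V1 and EOS, with clinical significance as a separate field. Reconcile this with Table 8-1 and 12.5.2.
2. **Check what was entered.** SAP version 2.1 (29-Apr-2025) describes randomisation in the past tense, so rewording alone probably comes too late for V1. Confirm from the eCRF and the database that these fields were completed. If not, enter them from the tracings that 8.4.2 requires sites to keep. Otherwise report the number of ECGs entered per arm and visit, and label the table as a selected subset.
3. **SAP 2.6.3.2.** Derive QTcF from QT and heart rate of the same tracing, state the formula, report it beside QT, and count QTcF > 500 ms by arm. Close the bracket in the variable list and restore any item that was dropped.

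Cost: no new ECG and one derived variable. If values were entered, the rest is a wording correction. If they were not, the most that could need entry is 2 × 900 = 1,800 tracings at the target sample size, at up to about 100 sites; the labelled-subset option avoids that work. How sites act on an abnormal ECG is unaffected.
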